4.4. End of Study Definition

The end of study is defined as when all participants have progressed, died, withdrawn consent, discontinued treatment due to other reasons, or have been lost to follow-up.

A participant will be considered to have withdrawn from the study if any of the following apply:

- The participant is lost to follow-up.
- The participant has withdrawn consent.
- The participant is no longer being followed at the investigator's discretion.
- The study is closed or terminated.

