6.6.1. Corneal Supportive Care Guidelines for Belantamab Mafodotin

Changes in visual acuity, which commonly manifests as changes in corneal epithelium observed on ocular examination, have been observed with antibody drug conjugates, including those conjugated to MMAF [Eaton, 2015].

Sites are required to establish a close collaboration with an ophthalmologist (or optometrist, if an ophthalmologist is not available) who will be responsible for assessing participants and managing those who develop corneal epithelium on ocular examination in close communication with GSK Medical Monitor.

Participants will be assessed by an ophthalmologist (or an optometrist if an ophthalmologist is not available) baseline and every three weeks. If there are no corneal examination findings (Grade 2 or above) at time of the Cycle 6 exam, participants may

have their ophthalmologic exams decreased to once every 3 months. In case of persistent ocular exam findings, newly developed ocular symptoms or vision changes, further ocular exams should be performed at least every cycle until resolution (to Grade 1 or baseline) or more frequently as clinically indicated by the qualified eye care specialist (Appendix 9). See Section 8.3.9 for the list of ophthalmic exam procedures.

Participants who have ocular symptoms at end of study treatment will continue to be followed as indicated in the SoA (Section 1.3) for up to 12 months, or until full resolution of findings: defined as a return to participant's baseline, or until deemed clinically stable by an ophthalmologist (or an optometrist if an ophthalmologist is not available), whichever comes first. Clinically stable is defined as changes less than or equal to Grade 1 as per Table 7.

Prophylactic preservative-free artificial tears should be administered in each eye at least 4 to 8 times daily, beginning on Cycle 1 Day 1 until EOT. Allow at least 5-10 minutes between administration of artificial tears and steroid eye drops (if administered). In the event of ocular symptoms (e.g., dry eyes), the use of artificial tears may be increased up to every 2 hours as needed.

While not yet clinically demonstrated, it is possible that the application of a cooling eye mask during belantamab mafodotin administration, and in the first few hours after infusion may subsequently decrease ocular side effects. On the day of infusion, at the discretion of the participant and the investigator, the following may be considered:

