8.3.3. Follow-up of AEs and SAEs

After the initial AE/SAE report, the investigator is required to proactively follow each participant at subsequent visits/contacts. All SAEs, non-serious AEs of special interest, will be followed until the event is resolved, stabilised, otherwise explained, or the participant is lost to follow-up (as defined in Section 7.3). Further information on follow-up procedures is given in Appendix 3.

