3.2. Final Analyses

The final planned primary analyses will be performed after the completion of the following sequential steps:

1. All participants have completed the study as defined in the protocol, i.e., when all participants have progressed, died, withdrawn consent, discontinued treatment due to other reasons, or have been lost to follow-up.
2. All required database cleaning activities have been completed and final database release (DBR) and database freeze (DBF) has been declared by Data Management.

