8.3. Adverse Events of Special Interest Analyses

Adverse events of special interest (AESI) for belantamab mafodotin are corneal events, thrombocytopenia and infusion related reactions.

Summaries of the number and percentage of participants with these events will be provided for each type of events separately by preferred term and maximum grade. The time of onset and duration of first occurrence of corneal events will be summarized using summary statistics mean, standard deviation, median, minimum value, and maximum. The number and percentage of participants who have time of onset of first occurrence (1-21, 22-42, 43-63, >63 days) will be reported. The number and percentage of participants who have duration of first occurrence (1-21, 22-42, >42 days) will be reported.

The summary of event characteristics of corneal events and thrombocytopenia will also be provided, including number of participants with any event, number of events, number of participants with any event that is serious, number of participants with any event that is related to study treatment, number of occurrences (One, Two, Three or more), maximum grade and the action taken for the event. The percentage will be calculated in two ways, one with number of participants with event as the denominator and the other with total number of participants as the denominator. The worst-case approach will be applied at participant level for the maximum grade, i.e. a participant will only be counted once as the worst case from all the events experienced by the participant. For action taken to an event, participant will be counted once under each action, e.g. if a participant has an event leading to both study treatment discontinuation and dose reduction, the participant will be counted once under both actions.

A comprehensive list of MedDRA terms based on clinical review will be used to identify each type of event. The details of the planned displays are provided in [Appendix 12: List of Data Displays](#).

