14.7.2.1. Handling of Missing and Partial Dates

Element	Reporting Detail
General	
 Partial dates will be displayed as captured in participant listing displays. Imputed partial dates will not be used to derive study day, duration (e.g. duration of adverse events), or elapsed time variables. In addition, imputed dates are not used for deriving the last contact date in the overall survival analysis dataset. Imputed dates will not be displayed in listings. However, where necessary, display macros may impute dates as temporary variables for the purpose of sorting data in listings only. In addition, partial dates may be imputed for 'slotting' data to study time periods or for specific analysis purposes as outlined below.
Adverse Events	
 The eCRF allows for the possibility of partial dates (i.e., only month and year) to be recorded for AE start and end dates; that is, the day of the month may be missing. 
 Missing Start Day: First of the month will be used unless this is before the start date of study treatment; in this case the study treatment start date will be used and hence the event is considered On-treatment as per Appendix 4: Study Phases and Treatment Emergent Adverse Events. Missing Stop Day: Last day of the month will be used. Completely missing start dates will remain missing, with no imputation applied. Consequently, time to onset and duration of such events will be missing. Completely missing end dates will remain missing, with no imputation applied. Consequently, duration of such events will be missing.
Concomitant Medications/Medical History	
 Partial dates for any concomitant medications recorded in the CRF will be imputed using the following convention: 
 If the partial date is a start date, a '01' will be used for the day and 'Jan' will be used for the month If the partial date is a stop date, a '28/29/30/31' will be used for the day (dependent on the month and year) and 'Dec' will be used for the month. The recorded partial date will be displayed in listings.
Covariates for efficacy analysis (Date of initial diagnosis/ Last recurrence/ Last progression)	
 If both month and day are missing, first of January will be used If only day is missing, first of the month will be used

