14.12.10. Safety Tables

Safety: Tables					
No.	Population	GSK Standard/ Example Shell	Title	Programming Notes	Deliverable [Priority]
Adverse Events (AEs)					
4.010	All Treated	AE13	Adverse Event Overview		SAC [1]
4.020	All Treated	AE3	Summary of All Adverse Events by Preferred Term		SAC [1]
4.030	All Treated	OAE07	Summary of All Adverse Events by Preferred Term and Maximum Grade		SAC [1]
4.040	All Treated	OAE07	Summary of All Treatment-Related Adverse Events by Preferred Term and Maximum Grade		SAC [1]
4.050	All Treated	OAE07	Summary of Non-Serious Adverse Events by Preferred Term and Maximum Grade		SAC [1]
4.060	All Treated	AE3	Summary of Adverse Events of Maximum Grade 3 or Higher by Preferred Term		SAC [1]
Adverse Events of Special Interest					
4.070	All Treated	OAE07	Summary of Corneal Events by Preferred Term and Maximum Grade		SAC [1]
4.080	All Treated	OAE07	Summary of Thrombocytopenia by Preferred Term and Maximum Grade		SAC [1]
4.090	All Treated	OAE07	Summary of Infusion Related Reactions by Preferred Term and Maximum Grade		SAC [1]
4.100	All Treated	ESI2b	Summary of Onset and Duration of the First Occurrence of Corneal Events		SAC [1]
4.110	All Treated	ESI1	Summary of Characteristics of Corneal Events		SAC [1]
4.120	All Treated	ESI1	Summary of Characteristics of Thrombocytopenia		SAC [1]
4.130	All Treated	AE3	Summary of Corneal Events Leading to Dose Modification by Preferred Term		SAC [1]
Serious and Other Significant Adverse Events					
4.140	All Treated	AE3	Summary of Serious Adverse Events by Preferred Term		SAC [1]
4.150	All Treated	AE3	Summary of All Treatment-Related Serious Adverse Events by Preferred Term		SAC [1]

CONFIDENTIAL

208465

Safety: Tables					
No.	Population	GSK Standard/ Example Shell	Title	Programming Notes	Deliverable [Priority]
4.160	All Treated	AE1	Summary of Adverse Events Leading to Dose Modification by System Organ Class and Preferred Term		SAC [1]
Laboratory: Chemistry					
4.170	All Treated	OLB9B	Summary of Chemistry Worst Grade Changes from Baseline Grade		SAC [1]
Laboratory: Hematology					
4.180	All Treated	OLB9B	Summary of Hematology Worst Grade Changes from Baseline Grade		SAC [1]
Laboratory: Hepatobiliary (Liver)					
4.190	All Treated	LIVER10	Summary of Hepatobiliary Laboratory Abnormalities		SAC [1]
ECG					
4.200	All Treated	EG1	Summary of ECG Findings		SAC [1]
4.210	All Treated	OECG1B	Summary of Worst-case Increases in Fridericia's QTc		SAC [1]

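### First corneal events still open at last contact get no duration under SAP 14.7.2.1, and Section 8.3 gives no ongoing or censored category, so the duration summary leans short by an unknown amount

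*SAP*

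**What the plan says.** SAP Section 8.3 plans mean, standard deviation, median, minimum and maximum for the time to onset and the duration of the first corneal event. It adds bands: "The number and percentage of participants who have duration of first occurrence (1-21, 22-42, >42 days) will be reported". The display is Table 4.100, "Summary of Onset and Duration of the First Occurrence of Corneal Events" (SAP 14.12.10), on shell ESI2b with an empty programming note.

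For adverse events without an end date, SAP 14.7.2.1 states: "Completely missing end dates will remain missing, with no imputation applied. Consequently, duration of such events will be missing". The general row of the same table also bars imputed partial dates from duration calculations, so an event with only a month and year for its end has no duration either.

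On how long an event is watched:

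- Protocol 8.3.3: serious events and non-serious events of special interest (corneal events are of special interest) "will be followed until the event is resolved, stabilised, otherwise explained, or the participant is lost to follow-up".
- Protocol 6.6.1: ocular symptoms present at end of treatment are followed "for up to 12 months, or until full resolution of findings", or until clinically stable, which is defined as Grade 1 or less.
- SAP 3.2: final analysis comes "when all participants have progressed, died, withdrawn consent, discontinued treatment due to other reasons, or have been lost to follow-up". Protocol 4.4 defines the end of study in the same way.

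The mock shells are held in separate documents (SAP 14.13).

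**The concern.** The SAP states a rule here; it is not merely silent. An event with no end date has no duration, and a participant with no duration cannot be placed in a duration band. An event known to be open at day 150 certainly belongs above 42 days, yet as written it enters neither the band nor the mean.

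Such events can arise with full protocol compliance. Follow-up may end at stabilisation, at 12 months, or at death, withdrawal or loss. Neither study end nor final analysis waits for open corneal events to resolve.

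Corneal events are the drug's most frequent adverse events (Protocol 2.3.2), and this is its first study in China. A table restricted to events that closed would suggest faster recovery than participants had. In the same SAP, duration of response is summarised by Kaplan-Meier where applicable (Section 7.2). Corneal duration has no comparable provision.

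**Working it through.** The plan gives no figure to reproduce. The check is of direction first, then of size under stated assumptions.

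**Direction.** Let D be the event's duration and C the time from its onset to the last date its status was known. The event has an end date only if D ≤ C. The table therefore estimates the mean of D given D ≤ C, which cannot exceed the overall mean of D when D and C are independent. The median and the share above 42 days move the same way.

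**Inputs from the protocol**

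- Onset of Grade 2 or above corneal findings at 2.5 mg/kg: median 36 days, range 19 to 143 (2.3.2).
- Time to resolution: median 91 days, range 21 to 201 (2.3.2).
- Median PFS, a proxy for time on treatment: 2.8 months (Phase II study, 2.5 mg/kg) or 12.0 months (first-in-human expansion part, 3.4 mg/kg) (2.3.1).
- 45 days: window for the end-of-treatment visit (1.3, footnote 4). 70 days: adverse event collection window (8.3.1). 365 days: about the 12-month ocular limit (6.6.1). 180 days: an intermediate value.

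**Assumptions.** Onset is lognormal and duration is Weibull with shape 2, each truncated to the range above. Progression time is exponential. Last dose falls on the last 21-day multiple before progression. Status is known until last dose plus the window. Each row uses 400,000 draws.

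| Median PFS (months) | Status known after last dose | Open | Mean, all → closed (days) | Median, all → closed (days) | Share >42 days, all → closed |
|---|---|---|---|---|---|
| 2.8 | 45 d | 50% | 95.3 → 81.4 | 91 → 75 | 0.89 → 0.83 |
| 2.8 | 70 d | 42% | 95.3 → 81.6 | 91 → 75 | 0.89 → 0.83 |
| 2.8 | 180 d | 4.5% | 95.2 → 91.9 | 91 → 88 | 0.89 → 0.885 |
| 12.0 | 45 d | 16% | 95.4 → 92.0 | 91 → 87 | 0.89 → 0.88 |
| 12.0 | 70 d | 13% | 95.2 → 91.8 | 91 → 87 | 0.89 → 0.88 |
| 12.0 | 180 d | 1.2% | 95.3 → 94.4 | – | – |
| either | 365 d | 0% | no shortfall | no shortfall | no shortfall |

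The largest shortfall in the mean is 95.3 − 81.4 = 13.9 days. At 180 days it is 0.9 to 3.3 days in these rows, and a repeat run gave up to 3.7. Lognormal durations give 13.5 and 3.5 days at the 45-day window. At 45 to 70 days, 46% to 70% of the dropped events were already known to exceed 42 days.

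**Sensitivity**

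- Short events (assumed median 21 days, range 3 to 90): the mean is 0.3 to 1.6 days short at 45 to 70 days.
- No 201-day cap, median still 91 days, with further treatment after onset of median 84 days plus 70 days: true means of 105 to 131 days fall to 73 to 86, with 24% to 30% open. The upper tail matters, and the documents do not settle it.

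**Six-event arithmetic.** Five events resolve with mean 91 days and one is open at day 150. The table reports 91. The true mean is at least (5 × 91 + 150) / 6 = 605 / 6 = 100.8 days.

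**The case against.** **The follow-up windows.** A reader might infer from the table above that up to half the events will be lost and the mean will be 14 days short. The documents do not support that as a forecast. The 45- and 70-day windows govern the end-of-treatment visit and adverse event collection. Corneal events are followed to resolution or stability (Protocol 8.3.3) and ocular symptoms for up to 12 months (6.6.1), with telephone contact for continuing visual symptoms (1.3, footnote 37). The larger figures apply only where death, withdrawal, loss or study end closes follow-up early. This stands.

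**The shells.** A reader might also infer that no planned display will show ongoing events. That cannot be established. Shell ESI2b is not visible. Nor is ESI1, used for the companion Table 4.110: its described contents run to "number of occurrences (One, Two, Three or more), maximum grade and the action taken for the event" with no outcome row mentioned, but Section 8.3 introduces that list as inclusions, so it need not be complete.

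**Clinical stability.** Stopping follow-up at Grade 1 need not leave an event without an end date, since the protocol elsewhere treats a return to Grade 1 or baseline as resolution for exam purposes. This also stands.

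**The inputs.** The 91-day figure is for Grade 2 or above findings, while Table 4.100 states no grade limit. The 2.8-month PFS comes from a more heavily pretreated population, and two participants here were still on treatment at Amendment 3.

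**Noise and disclosure.** With a duration SD of about 43 days and six events, the standard error is 43 / √6 ≈ 17.6 days, more than the largest modelled shortfall under the 201-day cap. The table is descriptive and no dose decision uses it. Listing 1.200 covers corneal events, and a shortfall in n could be noticed. These points lower the severity. They do not put an open event into the summary, and imprecision does not excuse a known direction of error.

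**Conclusion.** The point holds as a minor one. Under SAP 14.7.2.1 and Section 8.3 as written, first corneal events open at last contact leave the duration summary, and its mean, median and share above 42 days lean short.

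The size for this study is unknown, because the documents give no share of open events. With the protocol's external Grade 2 or above inputs and durations capped at 201 days, the mean is about 0 to 4 days short if ocular status is followed 6 to 12 months after the last dose, and up to about 14 days short if follow-up ends at 45 to 70 days. Longer tails would raise these figures and shorter events would lower them.

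The band problem does not depend on any of these assumptions: an event known to have passed day 42 has no route into the top band. The point does not imply that the protocol's ocular follow-up is inadequate or that any decision rule is affected. If ESI2b already carries an ongoing row, what remains is to align the SAP text with it.

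**What to change.** Change the SAP only, in Section 8.3 and the programming note for Table 4.100:

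1. Report the number and percentage of first corneal events not recorded as resolved at last contact.
2. Count those already open for more than 42 days in the >42-day band. Show the others in a row labelled *ongoing, 42 days or less*.
3. Put events recorded as resolved but with an unknown or partial end date in a separate row, *resolved, duration unknown*. They must not be coded as ongoing.
4. Label the mean, SD, median, minimum and maximum *resolved events with an end date only*.
5. Where data permit, add a Kaplan-Meier median, censoring at the last date the event's status was known (the later of the last ocular exam and the last adverse event follow-up contact; if a telephone date is not in the eCRF, the last exam or last visit with adverse event review).

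In Section 14.7.2.1, cross-reference Section 8.3 as an exception for first corneal events.

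The cost is SAP wording, a few rows and one statistic in one table. No visit, exam or protocol change is needed, and everyone already treated is covered. The Kaplan-Meier median will be imprecise with about six events: its simulated interquartile range was roughly 67 to 108 days, and it was not reached in 0% to 7% of simulated cohorts. The simple statistics remain restricted to closed events, but are labelled as such. The ongoing count and the band rule are the main gain.

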6.6. Concomitant Medications

Concomitant medications will be coded using GSK Drug coding dictionary, summarized, and listed. The summary of concomitant medications will show the number and percentage of participants taking concomitant medications by Ingredient. Multi-ingredient products will be summarized by their separate ingredients rather than as a combination of ingredients. Anatomical Therapeutic Chemical (ATC) classification Level 1 (Body

System) information will be included in the dataset created but will not appear on the listing or summary.

In the summary of concomitant medications, each participant is counted once within each unique ingredient. For example, if a participant takes Amoxycillin on two separate occasions, the participant is counted only once under the ingredient “Amoxycillin”. In the summary of concomitant medications, the ingredients will be summarized by the base only, using CMBASECD and CMBASE. Note: In order to be considered a concomitant medication, the concomitant medication must have been taken at some point during the on-treatment window.

Blood products or blood supportive care products with onset date within the on-therapy window will be included in the summary tables. The frequency and percentage of subjects using blood products and blood supportive care products after the start of study medication will be provided. Supporting listings will also be provided.

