14.4. Appendix 4: Study Phases and Treatment Emergent Adverse Events

14.4.1. Study Phases

Assessments and events will be classified according to the time of occurrence relative to the start and/or stop date of the study treatment. The earliest and latest exposure treatment start and stop dates will be used to determine whether an assessment or event was pre-treatment, on-treatment or post-treatment. If it is not possible to tell whether an assessment or event was on-treatment or not it will be considered as on-treatment.

Study Phase	Definition
Pre-Treatment	Date \leq Study Treatment Start Date
On-Treatment	Study Treatment Start Date $<$ Date \leq Study Treatment Stop Date + 70 days
Post-Treatment	Date $>$ Study Treatment Stop Date + 70 days

NOTES:

- Time of study treatment dosing and assessments and events should be considered, if collected, then the study phases will be re-defined as following:
Pre-Treatment: Date $<$ Study Treatment Start Date
On-Treatment: Study Treatment Start Date \leq Date \leq Study Treatment Stop Date + 70 days
Post-Treatment: Date $>$ Study Treatment Stop Date + 70 days

Concomitant Medication start and end dates will be assigned to study time periods in relation to first dose of study treatment as defined below. The start date references time flag variables and end date reference time flag variables will be added to the concomitant medication datasets, respectively.

- **Start relative to treatment:** Assign to 'BEFORE' if start date is prior to study treatment start date or if subject has not taken any study treatment or (start date is missing and end date is before study treatment start date). Else assign to 'DURING' if the start date falls into the on-treatment period as defined above or if subject is ongoing (not all study treatment discontinuation records completed) or start date is missing. Else assign to 'AFTER' if start date is after the on-treatment period.
- **End relative to treatment:** Assign to 'BEFORE' if end date is prior to study treatment start date or if subject has not taken any study treatment. Else assign to 'DURING' if start date falls into the on-treatment period or if subject is ongoing (not all study treatment discontinuation records completed) or (end date is missing and start relative to treatment not 'AFTER'). Else assign to 'AFTER' if start date is after the on-treatment period or (end date is missing and start relative to treatment='AFTER').

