14.12.4. Study Population Tables

Study Population Tables					
No.	Population	GSK Standard / Example Shell	Title	Programming Notes	Deliverable [Priority]
Subject Disposition					
1.010	All Treated	ES8	Summary of Subject Status and Reason for Study Withdrawal		SAC [1]
1.020	Screened	ES6	Summary of Screening Status and Screening Failures		SAC [1]
1.030	All Treated	SD1	Summary of Treatment Status and Reasons for Discontinuation of Study Treatment		SAC [1]
Protocol Deviation					
1.040	All Treated	DV1	Summary of Important Protocol Deviations		SAC [1]
Population Analysed					
1.050	Screened	SP1	Summary of Study Populations		SAC [1]
Demographic and Baseline Characteristics					
1.060	All Treated	DM1	Summary of Demographic Characteristics		SAC [1]
Disease Characteristics					
1.070	All Treated	DC2	Summary of Disease Characteristics		SAC [1]
1.080	All Treated	POP_T1	Summary of Genetic Characteristics and Cytogenetics Risk at Screening		SAC [1]
Medical Conditions					
1.090	All Treated	MH1	Summary of Current Medical Conditions		SAC [1]
Prior and Follow-Up Anti-Cancer Therapy					

Study Population Tables					
No.	Population	GSK Standard / Example Shell	Title	Programming Notes	Deliverable [Priority]
1.100	All Treated	POP_T3	Summary of Prior Anti-Cancer Therapy by Drug Class of Agents		SAC [1]
1.110	All Treated	POP_T4	Summary of Subjects Refractory to Prior Anti-Cancer Therapy by Drug Class		SAC [1]
Extent of Exposure					
1.120	All Treated	EX1 / EX5	Summary of Exposure to Belantamab Mafodotin		SAC [1]
1.130	All Treated	OEX6	Summary of Dose Reductions of Belantamab Mafodotin		SAC [1]
1.140	All Treated	OEX6	Summary of Dose Delays of Belantamab Mafodotin		SAC [1]
1.150	All Treated	Non-Standard	Summary of Dose Modifications of Belantamab Mafodotin		SAC [1]
Prior and Concomitant Medications					
1.160	All Treated	CM8	Summary of Concomitant Medications		SAC [1]
1.170	All Treated	CM8	Summary of Blood Products		SAC [1]
1.180	All Treated	CM8	Summary of Blood Supportive Care Products		SAC [1]

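### Incomplete start dates for blood products have no floor at first dose, so some support begun on therapy can drop out of Tables 1.170 and 1.180

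*SAP*

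**What the plan says.** SAP 14.7.2.1 opens its medication row with "Partial dates for any concomitant medications recorded in the CRF will be imputed using the following convention" and then gives the start-date rule: "If the partial date is a start date, a '01' will be used for the day and 'Jan' will be used for the month". Partial stop dates go to the end of the month or to December. The general row of the table confirms that "partial dates may be imputed for 'slotting' data to study time periods".

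The adverse-event row is different. For a missing start day, "First of the month will be used unless this is before the start date of study treatment"; in that case the treatment start date is used and the event counts as on-treatment.

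SAP 14.4.1 then flags medication starts: "Assign to 'BEFORE' if start date is prior to study treatment start date". A start inside the on-treatment period is DURING. So is a wholly missing start, unless the stop date is before treatment.

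SAP 6.6 sets the entry condition for the supportive-care tables: "Blood products or blood supportive care products with onset date within the on-therapy window will be included in the summary tables". These are Table 1.170 (blood products) and Table 1.180, the "Summary of Blood Supportive Care Products". SAP 14.12.4 lists both under prior and concomitant medications, with shell CM8.

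**The concern.** Taken together, these rules can move a product begun after first dose to a date before it. This happens when the recorded month or year is the one that contains first dose. The record then fails the onset condition in SAP 6.6, although that section sets out to report use of these products once study medication has started.

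Two features suggest an oversight and not a choice. An adverse event with the same partial date is kept as on-treatment. And a medication with no start date at all is normally kept, while one with a known month or year is lost.

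At stake is an undercount of supportive care at the first-dose boundary, in a small study of a drug for which thrombocytopenia is an adverse event of special interest (Protocol 8.3.8, SAP 8.3).

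**Working it through.** The documents give no figure on this point, so there is none to reproduce. The check applies the rules as written.

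**Inputs.** Imputation and AE floor: SAP 14.7.2.1. Flags and phase boundaries: SAP 14.4.1. Treatment-emergent definition: SAP 14.4.2. Table entry: SAP 6.6. Up to 6 evaluable participants per cohort and 12 in all: Protocol 4.1. Assumed: a 365-day calendar, 180 days of treatment, and a first dose on 10 March 2021 for the example.

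**Example.**

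| Recorded start | Imputed start | Medication flag |
|---|---|---|
| Mar 2021 | 1 Mar 2021 | BEFORE |
| 2021 | 1 Jan 2021 | BEFORE |
| Apr 2021 | 1 Apr 2021 | DURING |
| wholly missing | none | DURING |

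An adverse event recorded as Mar 2021 is moved to 10 March and is treatment-emergent.

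**Day missing, onset on or after first dose in the same month.** A month of n days has n(n+1)/2 pairs of first-dose day and onset day. Over the year: 7 × 496 + 4 × 465 + 406 = 5,738 pairs. First dose falls on the 1st in 365 of them. The other 5,373 are flagged BEFORE: 5,373/5,738 = 93.6%. By first-dose date, (365 − 12)/365 = 96.7% are exposed.

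**Day and month missing, onset in the year of first dose.** There are 49,775 pairs within 180 days. In 181 of them first dose is on 1 January. The other 49,594 are BEFORE: 99.6%.

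**Day missing, onset in a later month.** All 60,327 pairs are DURING, so these records are unaffected.

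**Size in the tables.** One participant lost is 1/6 = 16.7 points or 1/12 = 8.3 points.

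**Does an AE-style floor cure it?** A floored date equals the treatment start date. The date-only on-treatment definition in SAP 14.4.1 requires a date strictly after treatment start, while BEFORE requires a date strictly earlier, so the floored record gets neither flag: 0 of 5,738 recovered. With the inclusive boundary, which SAP 14.4.1 uses when times are collected and SAP 14.4.2 uses for adverse events, 5,738 of 5,738 become DURING.

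**What the floor costs.** Suppose dose day D and product start day E are independent and uniform over a 30-day month. Then P(E ≥ D) = 31/60 = 51.7% and P(E < D) = 29/60 = 48.3%. The current rule excludes nearly all of the first group. The floor would include the second group, less any record whose stop date shows it ended before treatment.

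**The case against.** The case against is mainly about reach, and much of it stands.

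- Only partly dated records are affected. Protocol 6.5 asks for start and end dates, and the schedule of activities reviews concomitant medications repeatedly in Cycle 1, so there may be few such records or none.
- The documents do not say that blood products use the medication date rule; they have their own paragraph in SAP 6.6 and their own listings (30.100, 30.110). The term blood supportive care products is not defined, so including growth factors is an inference.
- The floor exchanges one error for another. Under uniform dates the two are about equal, so the choice of direction has to be justified.

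A reader might also infer more than the documents support:

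- That the rule contradicts the fallback in SAP 14.4.1: "If it is not possible to tell whether an assessment or event was on-treatment or not it will be considered as on-treatment". That sentence covers assessments and events. Medications have their own flags, and imputation supplies a definite date. The rule is out of line with that default but does not strictly contradict it.
- That these are the only summaries of such support. Table 1.160 summarises concomitant medications by ingredient and accepts BEFORE starts that continue on therapy, so growth factors may also appear there. The listings show the recorded partial date.
- That the error runs only one way. At the end of the on-treatment window, the same rule can pull a late start into the on-therapy period.
- That it distorts the DLT assessment. DLTs are summarised from the DLT Evaluable population, not from these tables. The day-missing problem covers only the rest of the calendar month of first dose, not the 21-day window.

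**Conclusion.** The point holds as a small, cheap correction. If blood products follow the medication date rule, a partly dated product begun after first dose in that month or year is flagged BEFORE and left out of Tables 1.170 and 1.180. The exception is a first dose on the 1st of the month (or 1 January for year-only records), and even then the date-only boundary leaves the record without a flag. This is inconsistent with the treatment of wholly missing medication starts in SAP 14.4.1 and with the AE row of SAP 14.7.2.1.

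At the first-dose boundary the effect is an undercount. The tables count participants, so the shift of 16.7 points (n=6) or 8.3 points (n=12) needs a participant with no other on-therapy record. The number of partial dates is not given, so the realised effect is unknown and may be zero. DLT, AE, ORR and PK results do not depend on it.

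The conclusion rests on blood products falling under the medication row, which their placement and shell in SAP 14.12.4 support but do not state. The 93.6% and 99.6% are shares of enumerated date pairs, not predictions for this trial.

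**What to change.** In SAP 14.7.2.1, add to the medication row a rule that expressly covers blood products and blood supportive care products. If the recorded month (or year) of the start contains the treatment start date, and the stop date does not precede treatment start, set the start to the treatment start date and flag the record DURING. Otherwise keep the current rule. In SAP 14.4.1, make the lower boundary inclusive (treatment start date ≤ date) for these flags, as SAP 14.4.2 already does for adverse events; without this the floored records receive no flag.

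The cost is a short addition to each of two SAP sections and a small change to the derivation. No data collection or primary analysis is reopened. The downside is that some truly pre-dose products will be counted as on-therapy: up to about half of the affected records under uniform dates, fewer where the stop date is informative. That is the conservative direction the SAP already takes for adverse events.
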